### **8.2.7.6 Handling of Missing Items Within a Clinical Assessment**

The final scores of the ADAS-Cog, ADCS-ADLMCI, NPI, MMSE, CDR-SB, CCS-2D, and CCS-3D are all constructed from multiple subquestions/tests within each assessment. It is possible that one or more subquestions/tests may be missing within each overall assessment. In this event, the last recorded score for this subquestion(s) will be carried forward from the most recent postdose visit. (Last Observation Carried Forward approach). In a similar fashion, missing baseline values will be carried over from the most recent screening visit, if available. Baseline/screening values will never be carried forward to impute missing postdose values. Due to the degenerative properties of AD, with subjects expected to worsen over time, an individual subquestion will not be carried forward for more than one visit. If the same subquestion is missing two visits in a row, then LOCF will be applied to the first missing visit and the subquestion will remain as missing for the second visit (with the total score to then be computed as missing). Further, the total score will be computed as missing if too many subquestions, prior to applying the LOCF approach, are missing (see endpoint-specific details below). This single imputation approach allows the total score to be calculated using the strength of the other subquestions collected at that time, for that subject. The Sponsor believes this approach to be more accurate than either setting the entire score to missing or to imputing the worst possible score. More complicated missing data approaches are not thought to be warranted, since the amount of missing data within an assessment is expected to be extremely low.

For Baseline ADCS-ADLMCI only (from the initial 104-week trial): Past experience indicates that some subquestions on the ADCS-ADLMCI may mistakenly be omitted at the time of administration. Should this occur at baseline, there will be no opportunity to employ the stated LOCF approach. To avoid a missing total score on the ADCS-ADLMCI (and the subsequent removal of the subject from the primary ADCS-ADLMCI population), the worst possible score for that subquestion will be imputed. Note that this imputation approach will only be implemented for ADCS-ADLMCI (given the relatively small impact of the individual subquestions on the overall score) and only at baseline. A total score will only be computed if the number of missing subtotals is strictly less than three.

Endpoint specific details are as follows:

ADAS-Cog and MMSE: The site will be instructed to enter the worst possible score if the subject is unwilling or unable to answer a subquestion due to reasons related to the area the subquestion is trying to address. If the subject is unable to answer a subquestion for some

other reason, then the site will be instructed to leave the subquestion as missing. For both the ADAS-Cog and the MMSE, a total score will be calculated if the original number (prior to applying LOCF) of missing subtotals is strictly less than three.

CCS-3D: If no more than one test is missing within a domain(s), LOCF will be applied to that individual test. Values will not be carried forward for more than one visit. If more than one test is missing within a domain (prior to applying LOCF), then the overall z-score for that domain will be computed as missing. The overall CCS-3D will be computed as missing if any domain score is missing. Note that, in general and unless otherwise noted, the application of LOCF to these individual tests is solely for the computation of the domain z-scores and ultimately the CCS-3D. LOCF will not be applied to these individual tests for the analyses of the individual tests themselves (e.g., LOCF may be applied to the Delayed Word Recall test for the computation of the Episodic Memory domain z-score and ultimately the CCS-3D, but would not be applied for the purposes of analyzing the Delayed Word Recall component individually).

CCS-2D: If no more than one of the five component tests is missing, then LOCF will be applied to that individual test, solely for the purposes of computing the total score. If more than one of the component tests is missing, then the total score will be computed as missing.

CDR-SB, ADCS-ADLMCI, and NPI: The CDR-SB, ADCS-ADLMCI, and NPI are all administered to the trial partner, not the subject, so no within-assessment missing data are expected (though missing subquestion data is still possible due to data entry error or errors in test administration). For ADCS-ADLMCI and NPI, a total score will be calculated if the original number of missing subtotals is strictly less than three. For CDR-SB, a total score will be calculated if the original number of missing subtotals is strictly less than two.

### **8.2.8 Statistical Methods for Safety Analyses**

Subjects from all three arms (40 mg / 40 mg, 12 mg / 12 mg, Pbo / 40 mg) will be included in the safety analyses. Where applicable, treatment comparisons will be conducted between the 40 mg / 40 mg and Pbo / 40 mg arms, as well as between the 12 mg / 12 mg and Pbo / 40 mg arms.

Safety and tolerability will be assessed by clinical review of all relevant parameters including AEs, laboratory tests, vital signs, and ECG measurements. The primary approach for all safety analyses will be an On Drug approach, i.e., one that includes only those observations obtained from the first dose through 14 days after the last dose of study medication. A supportive approach will include all post-treatment observations, including those observations obtained more than 14 days after the last dose of study medication.

The analysis of safety results will follow a tiered approach (Table 7). The tiers differ with respect to the analyses that will be performed. Safety parameters or adverse experiences of special interest that are identified a priori constitute “Tier 1” safety endpoints that will be subject to inferential testing for statistical significance with p-values and 95% confidence intervals provided for between-group comparisons. Other safety parameters will be

considered Tier 2 or Tier 3. Tier 2 parameters will be assessed via point estimates with 95% confidence intervals provided for between-group comparisons; only point estimates by treatment group are provided for Tier 3 safety parameters.

Adverse experiences (specific terms as well as system organ class terms) and predefined limits of change in laboratory, vital signs, and ECG parameters (see Section 12.3) that are not pre-specified as Tier-1 endpoints will be classified as belonging to "Tier 2" or "Tier 3", based on the number of events observed. Membership in Tier 2 requires that at least 1% of the subjects in any treatment group exhibit the event; all other adverse experiences and predefined limits of change will belong to Tier 3.

The threshold of "at least 1%" was chosen because the expected number of subjects in the ASaT population is expected to be greater than 400 per treatment group. Thus an incidence of at least 1% in a treatment group translates to at least four subjects experiencing that event in the treatment group, which is the minimum number needed to attain statistical significance at  $\alpha=0.05$ . Because many 95% CIs may be provided without adjustment for multiplicity, the CIs should be regarded as a helpful descriptive measure to be used in review, not a formal method for assessing the statistical significance of the between-group differences in AEs and PDLCs.

Continuous measures such as changes from baseline in laboratory, vital signs, and ECG parameters that are not pre-specified as Tier-1 endpoints will be considered Tier 3 safety parameters. Summary statistics for baseline, on-treatment, and change from baseline values will be provided by treatment group in table format.

For this protocol, 1) microhemorrhage, superficial siderosis or macrohemorrhage; 2) vasogenic edema; 3) delirium; and 4) rash ECI (see Section 7.2.3.2 for definition) are considered as Tier 1 events. The broad clinical and laboratory AE categories consisting of the percentage of subjects with any AE, a drug related AE, a serious AE, an AE which is both drug-related and serious, and who discontinued due to an AE will be considered Tier 2 endpoints. A composite endpoint of hypopigmentation adverse events is defined based on the following preferred AE terms or equivalent: (noting that MedDRA terms are subject to change over time): skin hypopigmentation, skin depigmentation, vitiligo, leukoderma, hypopigmentation of eyelid, and idiopathic guttate hypomelanosis. This composite AE of hypopigmentation will be considered as either a Tier 2 or Tier 3 AE, per the criteria for Tier 2 AEs defined above. P-values (Tier 1 only) and 95% confidence intervals (Tier 1 and Tier 2) will be provided for between-treatment differences in the percentage of subjects with events; these analyses will be performed using the Miettinen and Nurminen method [27], an unconditional, asymptotic method.

The prespecified categories of suicidal ideation and behavior will be analyzed per the tiered analysis strategy outlined above, and will be considered as either Tier 2 or Tier 3 AEs, depending on the percent of events observed within each treatment group. Counts for each category will be based upon events observed during the assessment period (without consideration of prior history).

Safety analyses will only be based on subjects who treated in the long term trial. Unless otherwise noted, postdose data from the initial 104-week trial will not be analyzed with data from the long term trial.

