After initiation of the initial 104-week trial, the FDA issued guidance to sponsors indicating that all trials with BACE1 inhibitors that are longer than two weeks in duration must include routine monitoring of skin. Therefore, in order to gain additional data on those previously not exposed to MK-8931 during the initial 104-week trial, i.e. those subjects on placebo, routine skin examinations by a site physician will continue in this study. If no difference is seen in the occurrence of hypopigmentation between the placebo and MK-8931 groups after 300 subjects/group are evaluated at six months in the MK-8931 program (P017 and P019), the eDMC may recommend the discontinuation of the routine skin examinations. Sites would continue to collect skin-related adverse events and refer subjects for further dermatologic evaluation as needed.

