### **7.1.2.2.4 Skin Examinations**

To monitor for hypopigmentation, skin examinations will be performed by a site physician at the visits specified in Section 6.0, Trial Flow Chart. At Weeks 130, 156, 208, 260, 312, and 364, a site physician will perform a directed examination of the subject's skin. In addition, sites will instruct subjects to perform a self-examination of their skin between clinic visits (with the assistance of their trial partner, if needed). Subjects should report any abnormal loss of skin pigment to the site. The site physician's examination will focus on exposed skin and any areas of pigment loss noted by the subject or trial partner. If a clinically significant area of hypopigmentation is observed, the site should refer the subject to a dermatologist or medical expert for further follow-up. At each scheduled assessment, the following information should be recorded: whether significant sites of skin hypo- or depigmentation were observed, and any adverse events.

Based on the local standard of care, the investigator should refer subjects to a dermatologist or medical expert if: 1) a clinically significant area of skin develops hypopigmentation compared to baseline\*; or 2) if needed based on their clinical judgment. The following criteria are provided to guide the investigator but are not meant to be inclusive or to require referral in all cases.

- 1) A clinically significant area of hypopigmentation may include:
  - a) those greater than 3x3 cm
  - b) a smaller area (e.g., 1x1 cm) on the face or hands
  - c) a speckled pattern involving a larger amount of body surface area or
  - d) a smaller area (e.g., 1x1 cm) of complete pigment loss.

**Hypopigmentation for criterion 1** is defined as a decrease in skin color relative to the surrounding skin and its prior baseline appearance.

2) Clinical judgment criteria include:

- a) In the investigator's judgment, the hypopigmentation requires evaluation by an expert (e.g., small lesions on the face), or
- b) The subject or caregiver is distressed by the appearance of the skin lesion or hypo/depigmentation.

Dermatologists will evaluate and treat any lesions based on local standard of care. No special procedures are required per protocol.

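### The skin-examination result has no planned summary, and the hypopigmentation AE composite loses its confidence interval if incidence is below 1% in every arm

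*Combined protocol and SAP*

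**What the plan says.** **Purpose.** Section 4.2.2.2 keeps routine skin examinations in the extension "in order to gain additional data on those previously not exposed to MK-8931 during the initial 104-week trial", that is, the former placebo subjects. It also lets the eDMC recommend stopping them if no difference emerges across the program.

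**Measurement.** Section 7.1.2.2.4 sets the schedule: "At Weeks 130, 156, 208, 260, 312, and 364, a site physician will perform a directed examination of the subject's skin". At each one the site records "whether significant sites of skin hypo- or depigmentation were observed, and any adverse events". The finding and the AEs are two recorded items.

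**Analysis.** Section 8.2.8 opens its account of safety data with "Safety and tolerability will be assessed by clinical review of all relevant parameters including AEs, laboratory tests, vital signs, and ECG measurements". The skin-examination result is not named there, in Table 7 or in the predefined limits of change in Section 12.3. Hypopigmentation appears only as a composite of six AE preferred terms or equivalents: "This composite AE of hypopigmentation will be considered as either a Tier 2 or Tier 3 AE". The tier depends on the count: "Membership in Tier 2 requires that at least 1% of the subjects in any treatment group exhibit the event". For Tiers 1 and 2 a 95% interval for the between-arm difference is given, and "these analyses will be performed using the Miettinen and Nurminen method". Below the threshold, "only point estimates by treatment group are provided for Tier 3 safety parameters".

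**Population.** Extension safety analyses use only subjects treated in the extension (Section 8.2.8), in the arms 40/40, 12/12 and placebo/40.

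**The concern.** The protocol gives a reason for continuing a systematic examination and collects a yes/no result from it, but the plan never says how that result will be summarised. What it does analyse is an AE composite whose reporting depends on how many events occur. For an uncommon event, the interval shows how large an excess the data leave open, and the rule removes it when counts are low.

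There is a second mismatch. The stated interest is in the newly exposed, but every extension arm is on active drug. Even when the composite reaches Tier 2, the interval is for a difference between two active arms. It does not estimate incidence in the placebo/40 arm, and no interval for that incidence is planned.

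At stake is a secondary safety question: whether the extension report can say what hypopigmentation rate in newly treated subjects the data exclude.

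**Working it through.** **1. The plan's own threshold.** Section 8.2.8 justifies the 1% rule by expecting more than 400 subjects per group, so that 1% is at least four subjects, the minimum for significance at 0.05. The Miettinen-Nurminen method, two-sided with equal groups of 400, reproduces this: 4 v 0 gives p = 0.045 (95% CI 0.04 to 2.54 points) and 3 v 0 gives p = 0.083.

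**2. Group size in the extension.** Section 8.2.11.1.2 gives 1350 randomised, 25% dropout at Week 104 and 90% of completers continuing. 1350 × 0.75 × 0.90 = 911, in line with the 912 in Section 1.0, or about 304 per arm. Sizes of 300, 304 and 400 are carried forward because the 1% rule is a step. It needs ceil(0.01 × n) events: 3 at n = 300, and 4 at n = 304 or 400.

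**3. Chance that no interval is produced.** The composite is Tier 3 only if every arm has fewer than k = ceil(0.01n) events. With independent arms,

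P(no interval) = product over arms of P(X ≤ k − 1), X ~ Binomial(n, p).

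The documents give no hypopigmentation rate, so all rates below are assumed.

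| n per arm | k | P(X ≤ k−1), p = 1% | P(X ≤ k−1), p = 0.5% | No interval: 1%, 0.5%, 0.5% | No interval: all 0.5% | No interval: all 1% |
|---|---|---|---|---|---|---|
| 300 | 3 | 0.422 | 0.809 | 28% | 53% | 8% |
| 304 | 4 | 0.638 | 0.932 | 55% | 81% | 26% |
| 400 | 4 | 0.432 | 0.858 | 32% | 63% | 8% |

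At n = 304 with rates of 1%, 0.5% and 0.5%: 0.638 × 0.932 × 0.932 = 0.55. At n = 300: 0.422 × 0.809 × 0.809 = 0.28. Most of the gap between these two comes from the step from three required events to four.

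**4. What the missing intervals would show, at 304 per arm.**
- 0 of 304: exact upper 95% limit 1 − 0.025^(1/304) = 1.21%.
- 3 of 304 (0.99%, so Tier 3): exact 95% CI 0.20% to 2.86%.
- 3 v 0: Miettinen-Nurminen difference 0.99 points, 95% CI −0.27 to 2.86.
- 0 v 0: Miettinen-Nurminen 95% CI ±1.25 points.

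If no arm reached 1%, the plan would report only the point estimates.

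**5. Examined against treated.** If the 37% dropout at Week 130 is cumulative from randomisation, about 450 × 0.63 = 284 per arm reach the first scheduled examination, against 304 entering. Roughly 20 per arm would leave before it. The flow chart also places a skin examination at the early termination visit, so some of those 20 would be examined. The two denominators differ, but not by much.

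**The case against.** **The measurement is not simply discarded.** A reader might infer from the SAP's silence that examination findings are lost. The documents do not support that. Section 7.2 counts any new unfavourable sign as an AE, and item 12 of Section 7.2.3.2 makes AEs of clinically significant hypo- or depigmentation ECIs, reportable within 24 hours. The composite can also capture lesions found by self-examination between visits, and it survives if routine examinations stop. The list of assessed parameters in Section 8.2.8 is introduced as inclusive, not exhaustive. All of this stands. What remains is that the recorded yes/no result has no stated summary or denominator.

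**The AE percentage is a legitimate rate.** Percent of treated subjects is the SAP's ordinary AE denominator, so it would be wrong to say the composite yields no rate. It answers a slightly different question from a rate among subjects examined.

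**Tiering is pre-specified and reasoned.** Below four events, significance cannot be reached, and suicidality follows the same rule. But Section 8.2.8 itself calls the intervals descriptive and not a formal test, so the significance argument is a weak ground for withholding one. Table 7 already fixes five broad AE categories as Tier 2 whatever their count.

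**A between-arm test of the examination finding would mislead.** It is tempting to ask for a Miettinen-Nurminen comparison of that finding. Recorded findings may be prevalent: the skin baseline is screening, Month 6 or the end of the initial trial, so lesions from 104 weeks of active drug in 12/12 and 40/40 would confound the contrast with placebo/40. This objection succeeds, and the fix is limited accordingly.

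**The probabilities are fragile.** They rest on assumed rates and move sharply between 300 and 304 per arm. The 911 shows no deduction for the dementia progressors now excluded, so the actual size may be lower. A single headline figure would overstate what is known.

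**Conclusion.** The concern holds in a limited form. The SAP plans no summary of the skin-examination result that the protocol collects for a stated purpose, and the AE composite that stands in for it gets no interval if incidence is below 1% in every arm. On the assumed rates the chance of no interval runs from 28% to 55% (1%, 0.5%, 0.5%) or 53% to 81% (all arms 0.5%) for 300 to 400 subjects per arm. At a common rate of 1% it is 8% to 26%. Both the rates and equal, independent arms are assumptions; the suppression rule itself is in the text.

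A reader might go further and conclude that a clean result could not be told from an uninformative one. That is too strong: Tier 3 still reports estimates by group, and anyone with the counts and denominators can compute a limit. The fault is that the plan does not commit to showing it, and in no tier commits to an interval for the newly exposed arm. This is a modest safety-reporting gap, worth closing because it is cheap.

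**What to change.** In Section 8.2.8 and Table 7:

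1. List the hypopigmentation composite as Tier 2 whatever its count, so that the Miettinen-Nurminen 95% interval is always shown for the two planned comparisons. Add an exact (Clopper-Pearson) 95% interval for its incidence within the placebo/40 arm.
2. Add a descriptive table of the examination finding by arm, by scheduled visit and cumulatively, with subjects examined as denominator. Count only findings new since the end of the initial 104-week trial and show those already present at entry separately. Produce it for as long as routine examinations continue, with no between-arm inference.

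The cost is a few sentences of SAP text, one extra table and a few more unadjusted descriptive safety intervals. Item 2 uses results the protocol already has sites record, and needs each subject's skin status at the end of the initial trial to be available for linkage. No visit, examination or treatment rule changes.

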## 1.0 TRIAL SUMMARY

Abbreviated Title	A Long Term Safety and Efficacy Trial of MK-8931 (SCH 900931) in Subjects with Prodromal AD (APECS)
Trial Phase	III
Clinical Indication	Treatment of early (prodromal) AD
Trial Type	Interventional
Type of control	Not Applicable
Route of administration	Oral
Trial Blinding	Double-blind
Treatment Groups	MK-8931 12 mg MK-8931 40 mg
Number of trial subjects	All subjects who complete the initial 104 week trial and are willing and qualified to participate in the long term trial will be enrolled. Subjects who progress to dementia due to AD in the main 104 week study will not be permitted to move into the long term extension study. The actual number enrolled may vary depending on the number enrolled in the 104 week trial, the dropout rate, and the number of eligible subjects who consent to enroll. Based on the current sample size projection and estimated dropout rate (25%) for the initial 104 week trial, approximately 912 subjects would be enrolled. The total number of subjects enrolled in the extension will not exceed the total enrolled in the initial 104 week trial.
Estimated duration of trial	The duration of the long-term trial is expected to be up to approximately five years or until a) MK-8931 becomes commercially available (locally), or b) when the MK-8931 program is terminated (whichever comes first). Duration of the trial may be limited based on local regulation.
Duration of Participation	Expected maximum duration of no longer than 260 weeks (5 years after the first subject enrolls), with the duration of individual subject participation dependent on the timing of enrollment. Duration of participation may be limited based on local regulations. Subjects who do not complete the initial 104-week trial of MK-8931 protocol 019 will not be permitted to continue in this trial. In addition, subjects who are less than 75% compliant with trial medication during the initial 104-week trial will require Sponsor approval to participate in this trial. Subjects will be followed for at least 14 days following cessation of treatment.
Randomization Ratio	Not applicable to this trial.

A list of abbreviations used in this document can be found in Section 12.4.

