#### 7.1.4 Other Procedures

##### 7.1.4.1 Withdrawal/Discontinuation

When a subject discontinues/withdraws prior to trial completion, all applicable activities scheduled for the final trial visit should be performed at the time of discontinuation. Any adverse events which are present at the time of discontinuation/withdrawal should be followed in accordance with the safety requirements outlined in Section 7.2 - Assessing and Recording Adverse Events. Subjects who permanently discontinue from treatment will be discontinued from the trial.

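### Tier 1 and Tier 2 safety comparisons rest on crude percentages over variable on-drug time; they would be distorted, and could mask harm, if discontinuation differs between Pbo/40 and the drug-tolerant arms

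*Combined protocol and SAP*

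**What the plan says.** Section 8.2.8 gives p-values (Tier 1) and 95% confidence intervals (Tiers 1 and 2) for "between-treatment differences in the percentage of subjects with events", and "these analyses will be performed using the Miettinen and Nurminen method [27], an unconditional, asymptotic method". Section 8.1.2 and Table 7 agree. The primary approach counts observations from first dose to 14 days after last dose; a supportive approach counts everything after treatment starts. On who is included: "Safety analyses will only be based on subjects who treated in the long term trial".

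Follow-up is not fixed. Section 1.0 sets a ceiling of 260 weeks, "with the duration of individual subject participation dependent on the timing of enrollment". Section 7.1.4.1 adds: "Subjects who permanently discontinue from treatment will be discontinued from the trial". Section 5.8 drops the retrieved-dropout follow-up that the initial trial used. Section 5.6 is inconsistent. It removes subjects who stop treatment permanently from the trial, but its list of mandatory reasons for stopping treatment allows monitoring to go on afterwards.

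Exposure appears only in Section 8.2.15, as descriptive summaries by arm. The plan specifies no person-time rate, fixed-interval risk or time-to-event analysis for safety.

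**The concern.** A crude percentage depends on the event rate and on how long subjects are observed. Staggered entry should affect the arms about equally because they were randomised. Time on drug also depends on stopping, and here the arms differ by design. The 40/40 and 12/12 subjects enter after 104 weeks on drug and must have tolerated it (Section 5.1.2), while Pbo/40 subjects take their first active dose at extension entry. Section 8.2.8 compares each of the first two arms with Pbo/40.

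The arm that stops earlier has less time in which to show an event, so its crude percentage falls. Equal underlying rates could then look different, or a raised rate could look close to equal. Long-term safety is the first primary objective (Section 3.1) and is framed as these same between-arm comparisons.

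**Working it through.** **The plan's own figure.** Section 8.2.8 bases its 1% Tier 2 threshold on the "expected number of subjects in the ASaT population is expected to be greater than 400 per treatment group", so that 1% "translates to at least four subjects experiencing that event in the treatment group", the minimum for significance at 0.05. The Miettinen-Nurminen statistic at a null difference of 0, with 400 per arm, gives:
- 4 v 0: z = 2.004, p = 0.045
- 3 v 0: z = 1.734, p = 0.083

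The figure reproduces. The stated arm size does not fit the extension-only safety set. Section 1.0 says "approximately 912 subjects would be enrolled", which matches 1350 × 0.75 × 0.90 = 911, or about 304 per arm if split equally. Four is still the smallest count at or above 1% of 304, and 4 v 0 still gives p = 0.045.

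**Inputs from the documents.** Section 8.2.11.1.2 and Table 9 give 25% dropout at Week 104, 37% at Week 130 and 90% roll-over. Retention over the first 26 extension weeks is 0.63 / (0.75 × 0.90) = 0.933, a hazard of −2 × ln(0.933) = 0.138 per year. Held constant, this leaves about 50% on drug at 5 years. No rate is given by arm.

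**Assumptions, because the documents give no figures.** Event hazard λ of 0.01 to 0.10 per year, the same in both arms. Administrative follow-up uniform over 2 to 5 years. Discontinuation hazard μ of 0.10 per year in the reference arm and 1 to 2 times that in the other. Events and stopping are independent with constant hazards, and the 14-day tail is ignored.

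**Formula.** With s = λ + μ, crude incidence = (λ/s) × [1 − (e^(−2s) − e^(−5s)) / (3s)].

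Worked case, λ = 0.05:
- μ = 0.10: (0.05/0.15) × [1 − (0.7408 − 0.4724)/0.45] = 13.4%
- μ = 0.20: (0.05/0.25) × [1 − (0.6065 − 0.2865)/0.75] = 11.5%

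The spurious difference is 2.0 points. Mean time at risk (crude/λ) is 2.69 v 2.29 years, so the exposure-adjusted rate is 5.0 per 100 person-years in both arms. At λ = 0.10 the percentages are 24.8% v 21.3%, a difference of 3.5 points.

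| Discontinuation ratio | Spurious difference, λ = 0.01 to 0.10 |
|---|---|
| 1 | 0 |
| 1.25 | 0.1 to 1.0 point |
| 1.5 | 0.2 to 1.9 points |
| 2 | 0.4 to 3.5 points |

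With 304 per arm, a nominal 5% two-proportion test at ratio 2 rejects about 11% of the time (λ = 0.05) and 18% (λ = 0.10).

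**Sensitivity.** With the reference hazard at 0.138, and follow-up either 5 years for everyone or uniform over 2.5 to 5 years, the ranges are 0.2 to 1.9 points at 1.25, 0.3 to 3.7 at 1.5 and 0.6 to 6.7 at 2. They remain 0 at equal stopping.

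**Masking.** Let the arm that stops more have a true event hazard 1.5 times higher (0.075 v 0.05) in the 2-to-5-year model:
- Equal stopping (μ = 0.10 in both): 13.4% v 19.4%, crude risk ratio 1.44
- μ = 0.20 in the higher-risk arm: (0.075/0.275) × [1 − (0.5769 − 0.2528)/0.825] = 16.6%, crude risk ratio 1.23

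The exposure-adjusted ratio is 1.50 in both cases.

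**The limit of a rate.** Suppose instead that the event occurs only in the first 3 months, with the same 10% risk in both arms (hazard −ln(0.9)/0.25 = 0.421 per year). With μ = 0.10 v 0.20, crude percentages are 9.9% v 9.8%. Mean time at risk is 2.65 v 2.24 years, so the rates are 3.7 v 4.3 per 100 person-years, a spurious ratio of about 1.17.

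**The case against.** A reader might infer that exposure in fact differs between the arms and that the planned comparisons are therefore wrong. The documents do not support this. Table 9 uses one dropout rate for all arms, and under equal stopping the distortion is nil. Nor do they show which arm would stop earlier.

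A reader might also infer that exposure-adjusted rates should replace the crude percentages. The early-clustering example argues against that. A rate assumes a roughly constant hazard, which is least safe for events soon after first exposure, and Pbo/40 is the newly exposed arm. For the imaging events, scans are done only when clinically indicated (Sections 4.2.2.2 and 7.1.2.2.6), so time on drug is not time under detection.

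Other points stand in part:
- An event that leads to stopping is counted before the subject leaves, so crude percentages do not directly lose it.
- Differential stopping would be visible: discontinuation due to an adverse event is a Tier 2 comparison, reasons for discontinuation are tabulated (Section 8.2.9.1) and exposure is summarised by arm.
- The intervals are labelled descriptive, although on grounds of multiplicity. Tier 1 keeps inferential p-values.
- At ratio 2 the 2.0- and 3.5-point differences lie inside 95% half-widths of about 5.2 and 6.7 points with 304 per arm.

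Seeing that stopping differs does not correct the comparison. The supportive all-observations analysis adds little if subjects leave when they stop drug.

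**Conclusion.** The concern holds as a conditional one. The plan has no safety comparison that accounts for time at risk, although on-drug follow-up varies widely and the compared arms start the extension with different drug experience. If discontinuation differs, crude differences would mislead by an amount that depends on the assumed rates. In the main model it is at most 1.9 points for ratios up to 1.5 and 0.4 to 3.5 points at a ratio of 2; it is larger with longer follow-up or faster discontinuation. Masking matters more than a false signal: with doubled discontinuation, a crude risk ratio of 1.44 shrinks to 1.23 in the worked case.

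All event rates, arm-specific discontinuation rates and the 2-to-5-year follow-up are assumptions. The crude analysis is a legitimate description and should stay. What is missing is a pre-specified time-based companion. Whether stopping differs will be clear only when data are seen by arm, and an adjustment chosen then would be post hoc.

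**What to change.** Keep the Miettinen-Nurminen comparisons. In Section 8.2.8 and Table 7, add as supplementary analyses:

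1. Time-to-first-event cumulative incidence for Tier 1 events and the broad Tier 2 categories, with between-arm differences and confidence intervals at fixed times from the first extension dose, for example 6, 12 and 24 months. Censor at the end of the on-drug window and state the assumption this makes. Treating drug discontinuation as a competing event would bring the dependence on stopping back in.
2. Exposure-adjusted incidence rates per 100 person-years on drug, with intervals for the difference, for Tier 1 and Tier 2 events.
3. A sentence saying that the rates are read alongside the curves and not alone, because they assume a roughly constant hazard.

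Reconcile Section 5.6, where monitoring may go on after treatment is stopped, with Section 7.1.4.1 and with Section 5.6's own statement that such subjects leave the trial. This settles what the supportive all-observations analysis can contain. While editing, align the stated arm size of more than 400 with the projected enrolment of about 912.

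The cost is SAP text and more tables, from dose and event dates already collected. The change should be made before the sponsor is unblinded at the end of the initial 104-week trial (Section 8.2.1).
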